5.2.2 Analysis of binary secondary outcomes

Binary secondary outcomes recorded on a daily basis will be analysed using a three-level mixed logistic regression model with the same levels and covariates as described in the mixed linear models above (§5.2.1). Depending on the convergence of the model and frequency of the outcomes, these variables may be simplified into a single binary variable across the entire admission (for example, a binary variables representing suicide risk any time during the admission).

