1.3 Objectives

1.3.1 Primary objective

The trial will test whether the environment with programmable lighting conditions offers any additional benefits beyond those associated with standard treatment in an acute psychiatric inpatient unit. Specifically, participants will be allocated to a ward with a lighting system that produces an environment with blue-depleted evening light or to a ward with the same layout and facilities but lacking the new lighting technology. The main objective is to examine if there is any difference between groups in the mean duration of hospitalization.

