2.2 Randomization and treatment assignment

A detailed description of the randomisation procedure can be found in the published protocol. Briefly, there will be a 1:1 block randomisation with varying block sizes, using the webCRF program (developed and managed at the Clinical Research Unit Central Norway). Patients who may need admission to the acute psychiatric hospital unit will initially be assessed by other health professionals (general practitioners, out-of-hours emergency services, and other somatic and psychiatric hospital departments). If hospitalisation is deemed necessary, patients will be directed to the acute admissions facility. For the purposes of the trial, patients will be randomised prior to arrival at the unit (i.e. prior to any psychiatric assessment at the acute unit). Clinical considerations may mitigate against following the random allocation procedure, in which cases some participants may be withdrawn immediately from the trial (see section §3.2.2).

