2.3 Determination of sample size

The sample size calculation is described in detail in the published protocol¹.

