3.1 Confidence intervals and p-values

All efficacy and safety estimates will be presented with two-sided 95 % confidence intervals. Accompanying two-sided p-values will be calculated and compared to a 5 % significance level. No adjustments for multiplicity will be made since there is only one primary null hypothesis in this trial. This is in line with “Guideline on multiplicity issues in clinical trials EMA/CHMP/44762/2017”.

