5.2.1 Analysis of continuous secondary outcomes

For continuous variables measured only at discharge (iCGI-I and measure of satisfaction), between group comparisons will be conducted using linear regression adjusting for the same covariates as the in the primary analysis.

The remaining continuous variables are measured two or more times per admission, and these will be analysed using a mixed linear regression model. Where possible, we will use a three-level linear mixed-model with respective secondary outcome as the dependent variable, timepoint (or day of admission) as level 1, admissions within patient as level 2, and patient as level 3. The covariates will include treatment allocation, the prespecified baseline variables and an interaction term between treatment and day of admission. If the model fails to converge, we will consider removing the interaction term and or reduce the number of levels.

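### The any-time-during-admission fallback for daily binary outcomes counts status recorded before the first evening of allocated light, which attenuates those secondary results

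*SAP*

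**What the plan says.** Randomisation comes first: "patients will be randomised prior to arrival at the unit" (SAP §2.2). The active arm is a ward whose lighting "produces an environment with blue-depleted evening light" (§1.3.1).

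Table 1 in §5.2 gives suicide risk, continuous observation, medication use and SOAS-R (all daily) and the Brøset checklist (8-hourly) the whole admission as timeframe. Suicide risk and observation are to be analysed by logistic models, medication by logistic or linear models, and Brøset and SOAS-R by linear models.

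For the repeated models, §5.2.1 states: "The covariates will include treatment allocation, the prespecified baseline variables and an interaction term between treatment and day of admission". If the model does not converge, the interaction may be removed or the number of levels reduced. §5.2.2 carries the same covariates over to binary outcomes. It adds that, depending on convergence and on how frequent the outcome is, a variable may be "simplified into a single binary variable across the entire admission (for example, a binary variables representing suicide risk any time during the admission").

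No section opens an outcome window after the first evening. The one exposure rule, two consecutive evenings, defines the per-protocol set (§3.3.2), and §5.1.3 applies that set only to the primary and subgroup analyses.

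**The concern.** For a patient who arrives before evening, ratings up to that evening precede any difference in light. Once the outcome is collapsed over the whole stay, a patient rated at suicide risk on arrival is an event whatever the light does afterwards. Such patients add the same expected amount to both arms and push the comparison towards no difference. Status at arrival is not among the §5.1 covariates, although §4.2 tabulates risk of harm at presentation.

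At stake is the reading of secondary outcomes: a real reduction in suicide risk or need for observation could be reported as little or no effect because arrival status was counted as outcome.

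**Working it through.** **Inputs.** The documents give 1:1 allocation (§2.2), a two-sided 5% level (§3.1), randomisation before arrival, and evening light. The SAP states no sample size ("The sample size calculation is described in detail in the published protocol", §2.3) and no figure for any secondary outcome, so there is no stated figure to reproduce. All rates, correlations and group sizes below are assumptions.

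**1. Collapsed binary outcome.** Let p0 be the share positive before the first evening (equal across arms in expectation) and q the risk of new onset among the rest.

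P(any time) = p0 + (1 − p0)q, so the difference between arms is (1 − p0)(q_normal − q_blue).

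With q = 20% (normal) v 12% (blue-depleted):

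| p0 | Normal | Blue-depleted | Difference (points) | Odds ratio |
|---|---|---|---|---|
| 0% | 20.0% | 12.0% | 8.0 | 0.55 |
| 5% | 24.0% | 16.4% | 7.6 | 0.62 |
| 20% | 36.0% | 29.6% | 6.4 | 0.75 |
| 40% | 52.0% | 47.2% | 4.8 | 0.83 |
| 60% | 68.0% | 64.8% | 3.2 | 0.87 |

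Example at p0 = 40%: 0.4 + 0.6 × 0.20 = 0.520; 0.4 + 0.6 × 0.12 = 0.472; odds ratio (0.472/0.528)/(0.520/0.480) = 0.83.

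**2. Power.** Second illustration: new onset 20% v 10%, 200 per arm. For the any-time variable, power is 80%, 57%, 40%, 30% and 17% at p0 = 0, 10%, 20%, 30% and 50%. Counting new onset only among those negative at arrival gives 76%, 71%, 65% and 51% at p0 = 10%, 20%, 30% and 50%.

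**3. Keeping everyone, but counting only after the first evening.** The gain then depends on those already positive. At p0 = 20%, if their status persists in 60% v 45%, the difference is 0.2 × 0.15 + 0.8 × 0.10 = 11.0 points (power 75%), against 8.0 points (40%) for the any-time variable. If the light does not change persistence, the crude difference is again 0.8 × 0.10 = 8.0 points, and any gain must come from adjusting for earlier status.

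**4. Repeated continuous outcomes with the interaction dropped.** If one of L daily ratings precedes exposure, the effect on the whole-stay mean is multiplied by (L − 1)/L: 67%, 80%, 90% and 93% for L = 3, 5, 10 and 14. An 8-hourly score gives 3 × 5 = 15 ratings over five days. With one or two of them before the first evening, 14/15 = 93% or 13/15 = 87% of the effect remains.

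A simulation of a random-intercept model (40 replicates, 150 per arm, true effect −0.30 after day 1, within-admission correlation 0.5) gave:
- all days, no interaction: −0.23 (SE 0.091)
- later days, adjusted for the first value: −0.31 (SE 0.076)
- first value kept as outcome, arms constrained equal at that timepoint: −0.31 (SE 0.076)

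The simulation error of these means is about 0.091/√40 = 0.014 and 0.076/√40 = 0.012, so −0.31 agrees with −0.30. The §5.1 covariates were not simulated, so the gain in precision over the actual plan may be smaller.

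**The case against.** The timing is partly inferred. The SAP does not say at what hour daily items are rated, and §2.7 defers to Table 1 of the published protocol, which was not available for this check. Patients who arrive in the evening or at night may have no pre-exposure rating. This narrows the point to earlier arrivals but does not remove it.

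The collapse is conditional. The first-choice model has a treatment-by-day interaction, in which early ratings anchor the trajectory. If rarity is what triggers the collapse, p0 is probably small and the loss slight (8.0 to 7.6 points at 5%). Both arguments stand and limit the size. However, §5.2.2 also names convergence as a trigger, and that can occur with a common outcome.

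In a pragmatic trial of ward allocation, risk over the whole admission is a legitimate quantity. That is fair, but it does not justify leaving arrival status out of the model.

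A reader might infer several stronger things that the SAP does not support:
- *Every during-admission estimate is diluted.* Change of admission status conditions on involuntary admission (Table 1, note b) and adjusts for admission status (§5.1). The iCGI-I is a change score, sleep is measured mainly after an evening, and adherence has no pre-exposure value.
- *The collapse distorts the aggression results.* Brøset and SOAS-R are linear outcomes, so §5.2.2 does not reach them; only dropping the interaction does.
- *Using the arrival value as an outcome is itself an error.* With the arms constrained equal at the first timepoint it did as well as adjustment. The SAP simply states no such constraint.
- *Severity at arrival is uncorrected.* Diagnosis, comorbidity, legal status and prior admissions are adjusted for; the pre-exposure value of the outcome itself is not.

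**Conclusion.** The point holds for the collapsed binary outcomes (suicide risk, continuous observation, binary medication use). It holds to a smaller degree for Brøset and SOAS-R if the interaction is removed. For the collapsed outcomes the difference in new onset is multiplied by (1 − p0). That factor is exact when positive status before the first evening counts as an event, but p0 cannot be found from the SAP. Over an assumed 5% to 60%, a difference of 8.0 points becomes 7.6 to 3.2.

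The 8.0 points, like the odds ratio of 0.55, refer to patients not yet positive. They are not a forecast of what a corrected analysis of all patients would show. How strongly the arrival value predicts later ratings is also an assumption.

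Randomisation balances pre-exposure status in expectation, so the harm is attenuation and lost precision, not a false effect. Only secondary outcomes are involved; the analysis of duration of admission is untouched. The change is worth making because it is cheap and the data are already collected.

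**What to change.** Amend the SAP before the statistician is unblinded, a route that §3.4.2 already provides:

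1. In §5.2.2, define any collapsed binary outcome as occurrence after the first evening on the allocated ward, adjusted for status before that evening.
2. In §5.2.1 and §5.2.2, for repeated outcomes with pre-evening ratings, treat those ratings as baseline, either as a covariate or with the arms constrained equal at the first timepoint. Name the treatment contrast to be reported, including when the interaction is dropped.
3. Where an evening or night arrival has no earlier rating, use the presentation risk from health records (§4.2) where it matches the outcome, or state a missing-baseline rule. The records have a further merit: ward ratings follow allocation in an unblinded trial.

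The cost is SAP wording and some analysis work, with no new data collection. Admissions that end before the first evening contribute no post-exposure rating to these outcomes and should be counted per arm. Some baselines will be missing.

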5.2.3 Missing data

We anticipate a high level of missing data for some secondary outcome variables. Under the assumption that they are “missing at random”, the estimates produced by the mixed regression analyses should provide unbiased estimates of the effect of the lighting conditions on these secondary outcomes. For secondary outcomes that cannot be analysed using mixed regression modelling (i.e. those with only one measurement or those simplified to a single summary measure), we will use multiple imputations to handle missing data as appropriate.

5.2.4 Additional analyses

Subgroup analyses based on psychiatric diagnostic groups are planned for each of the secondary outcomes. Other exploratory subgroup analyses for on the covariates listed in §5.1 will also be considered, particularly if they are found to be important sources of treatment effect heterogeneity for the primary outcomes. These subgroup analyses may be presented in subsequent manuscripts after publication of the primary trial results.

5.3 Analysis of safety outcomes

As specified in the published protocol, the frequency of any side effects or adverse events will be recorded during the trial period. The eight-item Headache and Eye Strain (HES) Scale will be specifically used at discharge to measure adverse effects due to lighting conditions⁵, along with another eight-item scale reflecting side effects of acute psychiatric treatments. The average value of these scores will be compared between groups using a t-test. Other reported adverse events will be summarised as binary variables and analysed using Chi-squared test. This will include an analysis of the proportion of patients which were transferred from their allocated ward after clinical opinion. For any adverse events occurring multiple times per participant per admission we will consider alternative statistical analyses such as Poisson regression.

STATISTICAL ANALYSIS PLAN for BAB-study

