3.2.3 Protocol deviations

During the admission withdrawal may occur because:

- The participant is absent for >24 hours from the ward to which they were randomised, for example due to transfer to another hospital for medical/somatic reasons. Any participant who is absent from the ward voluntarily is considered to have been discharged and if they were to return they would be re-randomised and recorded as another admission.
- Clinical concerns regarding an individuals' participation

These scenarios will be considered protocol deviations, and the participants will be removed from any per-protocol analyses (see also §3.3.2).

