5.1 Analysis of primary outcome

The primary outcome is duration of admission in days in the ITT population. Some patients will be readmitted and re-randomized during the study period. As such, we plan to use a two-level linear mixed-model with duration of stay as dependent variable, with admissions within patient as level 1, and patient as level 2. The primary covariate is group (blue-depleted evening lighting versus normal lighting condition). We will adjust the analyses for a set of pre-specified baseline variables which can be strong predictors of the outcome, as generally recommended by Kahan et al³ and Vittinghoff et al⁴.

These covariates are:

- Age
- Sex
- Diagnosis (categorized as psychotic episodes/disorders, manic episode, severe depressive episode, or none of these)
- Comorbidities (categorized as alcohol/substance use disorders, borderline or other personality disorders, or none of these two)
- Involuntary versus voluntary status at admission
- Number of admissions in the previous 2 years
- Number bed-days in the previous 2 years.

If the model fails to converge using a two-level model we will consider a single-level model.

As this primary outcome is heavily skewed and not normally distributed, we anticipate the use of bootstrapping with the bias-corrected and accelerated (BC_a) method and B=5000 bootstrap samples. If this results in unpractical long computing time, we will use a lower number of bootstrap samples, such as B=1000.

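### Four discharge and safety scores drop the patient level that SAP §5.1 uses for readmitted patients, which costs some precision but not validity

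*SAP*

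**What the plan says.** SAP §5.1 expects repeat admissions: "Some patients will be readmitted and re-randomized during the study period". For that reason it plans a "two-level linear mixed-model with duration of stay as dependent variable, with admissions within patient as level 1, and patient as level 2". It adds covariates: "We will adjust the analyses for a set of pre-specified baseline variables which can be strong predictors of the outcome". SAP §3.2.3 says of patients who leave voluntarily that "if they were to return they would be re-randomised and recorded as another admission".

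SAP §5.2.1 keeps the patient level for continuous outcomes measured two or more times per admission, and §5.2.2 does so for daily binary outcomes. For iCGI-I at discharge and satisfaction it says that "between group comparisons will be conducted using linear regression adjusting for the same covariates as the in the primary analysis". That keeps the covariates but has no patient level.

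SAP §5.3 has neither. For the Headache and Eye Strain score and the side-effect score: "The average value of these scores will be compared between groups using a t-test". Other adverse events are reduced to binary variables and compared by chi-squared test. One of these is the share of patients moved off their allocated ward on clinical opinion.

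SAP §5.2.3, on missing data, treats outcomes with a single measurement as outside the reach of mixed regression and assigns them multiple imputation.

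**The concern.** The same set of admissions is modelled in two ways. The feature that leads §5.1 to a patient level, several admissions from one person, is equally present in the four scores taken at discharge. The apparent justification in §5.2.3 does not separate the cases: length of stay also has one value per admission, and §5.1 puts it in a mixed model. The second level there comes from admissions within a patient, not from repeated measurements within an admission.

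What is at stake is precision. When a patient is admitted more than once, sometimes to different arms, the within-patient contrast carries information that a t-test or single-level regression does not use. This matters most for the Headache and Eye Strain scale, which §5.3 singles out for detecting harm from the lighting.

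The unit of analysis in §5.3 is also left open. A proportion of patients by arm is not defined for someone randomised to both arms.

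**Working it through.** **Inputs.** From the SAP: 1:1 allocation (§2.2), re-randomisation of each return (§3.2.3, §5.1), two-sided 5% level (§3.1). The SAP gives no readmission share, ICC, standard deviation or power for these scores, so there is no stated figure to reproduce. Assumed: shares of patients with 1, 2 and 3 admissions of 88/10/2% (12% readmitted) or 75/20/5% (25% readmitted), and ICC ρ of 0.2, 0.3 or 0.5.

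**Step 1: is the single-level test valid?** Code allocation T as ±½. The error of the difference in means is about (4/N) Σ Tε. For two admissions of one patient the cross-term is E[T₁T₂]·Cov(ε₁,ε₂). Independent allocations make E[T₁T₂] = 0. The variance is then (16/N²)·N·(σ²/4) = 4σ²/N, which is what the t-test assumes. Simulations of this design (400 patients, 3,000 runs per setting, ICC 0.2 to 0.7) agree: the t-test rejected in 4.5% to 6.0% of null trials.

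**Step 2: information with the patient level.** A patient with k admissions contributes trace(V⁻¹)/4 to the two-level model, against k/4 to the single-level one, where

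trace(V⁻¹) = 1/(1+(k−1)ρ) + (k−1)/(1−ρ).

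For ρ = 0.5 this is 1 (k=1), 2.667 (k=2) and 4.5 (k=3).

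- 12% readmitted: (0.88 + 0.10×2.667 + 0.02×4.5) / (0.88 + 0.20 + 0.06) = 1.237/1.14 = 1.085.
- 25% readmitted: (0.75 + 0.20×2.667 + 0.05×4.5) / (0.75 + 0.40 + 0.15) = 1.508/1.30 = 1.160.

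| ICC | 12% readmitted | 25% readmitted |
|---|---|---|
| 0.2 | 1.011 | 1.021 |
| 0.3 | 1.026 | 1.049 |
| 0.5 | 1.085 | 1.160 |

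**Step 3: in terms of power.** A comparison with 80% power under the single-level test has power Φ(2.802√r − 1.960) at information ratio r. That is about 80% at 1.011, 81% at 1.026, 83% at 1.085 and 85% at 1.160.

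**Step 4: outside that range.** If a share f of patients has two admissions and the rest one, the variance ratio is (1+f)/[(1−f)+2f/(1−ρ²)]. It runs from 0.99 (f = 10%, ρ = 0.2) to 0.69 (f = 30%, ρ = 0.7). The gain is negligible with few returns and large only with many returns and strong correlation.

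**Step 5: covariates.** Adjustment multiplies the variance by about 1−R². That is 0.90 at R² = 0.1 and 0.70 at R² = 0.3, but both values of R² are assumed. SAP §3.3.3 presents the covariates as predictive of length of stay and says nothing about headache, eye strain or side effects.

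**The case against.** The planned tests are valid under re-randomisation, and they concern secondary and safety outcomes. The gain from a patient level is modest and rests wholly on assumed inputs. The calculation also treats the ICC as known and every admission as observed. §5.2.3 expects much missing data in some secondary outcomes, which would leave fewer complete within-patient sets. With most patients admitted once, the patient variance is weakly estimated. The two-level model also reweights: at 25% readmitted and ICC 0.5, readmitted patients' share of the information rises from 0.55/1.30 = 42% to 0.758/1.508 = 50%. This matters if the effect differs in them. On the unit, §5.3 elsewhere speaks of events per participant per admission, so the admission is already the only workable reading.

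All of this stands as a limit on size. It does not explain why the plan should use its own model for one single-value outcome and rule it out for others. The unit needs only a clarification, but the present wording does not supply it. The covariate gain for the safety scores cannot be claimed as a figure.

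**Conclusion.** The plan is inconsistent, and the consequence is a modest loss of precision: about 1% to 16% of information for 12% to 25% of patients readmitted and ICC 0.2 to 0.5. Covariates may add to this by an amount that the SAP does not allow one to state. This is a desirable improvement, not an error that threatens the conclusions.

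A reader might infer that ignoring the patient inflates false positives, as it does when whole clusters receive one treatment. The SAP does not support that, because each return is randomised afresh. A reader might also infer that the post-randomisation removals in §3.2.2 undo this protection. They would have to make one patient's retained allocations alike across stays, and nothing in the SAP shows that. Nor is the change free, as set out below.

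The point covers iCGI-I at discharge, satisfaction and the two safety scores, together with the binary adverse events. CGI-S is recorded at baseline and discharge, so it already falls under the mixed model.

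**What to change.** - In §5.2.1 and §5.3, analyse iCGI-I at discharge, satisfaction, the Headache and Eye Strain score and the side-effect score with the two-level model and covariates of §5.1, keeping its single-level fallback.
- In §5.2.3, remove the premise that an outcome with one measurement cannot be analysed by mixed regression. Multiple imputation can remain available, with the patient level carried into the imputation model.
- In §5.3, name the admission as the unit of analysis. Analyse binary adverse events with logistic regression clustered on patient, by GEE or a mixed model, and keep chi-squared as the fallback for sparse events. Choose between GEE and the mixed model in advance, since their odds ratios differ in meaning.
- §4.2 records diagnosis at discharge. Use it as a covariate only if it is fixed at admission.

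The cost is a few sentences of SAP text and re-use of the primary model's code. No new data are needed, and §5.1.1 expects the covariates to be nearly complete. The downside is slightly more complex reporting and possible non-convergence, mainly for rare events.

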2.4 Framework

This trial is designed to establish the superiority of blue-depleted evening lighting environment compared to normal lighting on the duration of admission to acute psychiatric wards:

- The primary null hypothesis is that the duration of admission does not differ between the lighting environment group
- The primary alternative hypothesis is that the duration of admission differs based on the lighting environment.

There is only one primary outcome in this trial. The other efficacy analyses will be regarded as secondary or exploratory.

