5.1.1 Missing data

The primary outcome is based on hospital records of date of admission and date of discharge and will have no missing data. Similarly, the baseline variables included in the adjusted model should not have any missing data, perhaps with the exception of the number of admissions and numbers of bed-days in the previous 2 years if the patient has recently moved to the Trondheim region. If this occurs, we anticipate that very few participants will have missing information for these variables. The need to employ missing data strategies, such as multiple imputations, will be considered depending on the proportion of missing information.

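### SAP §5.3 compares other adverse events by default as per-admission proportions and names no exposure term, although the time at risk is the length of stay, the primary outcome.

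*SAP*

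**What the plan says.** SAP §5.3 covers three kinds of safety data. The headache and eye strain scale and a second side-effect scale are scored at discharge and compared by t-test; they are not at issue here. For the rest, the default is: "Other reported adverse events will be summarised as binary variables and analysed using Chi-squared test". Ward transfer is given as an example: "This will include an analysis of the proportion of patients which were transferred from their allocated ward after clinical opinion". The section ends with a conditional alternative: "For any adverse events occurring multiple times per participant per admission we will consider alternative statistical analyses such as Poisson regression".

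No offset, patient-day denominator, time-to-event method or fixed observation window is named in §5.3. Elsewhere, §5.1 makes duration of admission the primary outcome, and §2.4 states: "The primary alternative hypothesis is that the duration of admission differs based on the lighting environment".

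**The concern.** An adverse event on the ward can be recorded only while the patient is there. If the lighting shortens the stay, that arm has fewer days in which an event can occur, and the proportion with an event falls even if the risk on each day is unchanged. A higher daily risk in that arm would be understated for the same reason.

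The comparison is therefore hardest to interpret when the trial succeeds on its primary outcome. A reader of the safety table could take fewer affected admissions as better tolerability when it reflects fewer days observed. The Poisson sentence does not close this gap. It is optional, covers recurrent events, and leaves the offset unstated; a count model without an offset depends on length of stay in the same way.

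**Working it through.** **Inputs.** The SAP gives no length of stay, event rate, effect size or sample size, so there is no figure of its own to reproduce. Every number below is an assumption chosen to show direction and rough size.

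**Step 1: closed form.** Take a constant daily event rate r, the same in both arms, and exponentially distributed stays with mean L. Then P(at least one event) = rL/(1 + rL), and the odds are rL. With r = 0.05 and mean stays of 10 and 8 days:
- Longer-stay arm: 0.5/1.5 = 33.3%.
- Shorter-stay arm: 0.4/1.4 = 28.6%.
- Risk ratio 0.86; odds ratio 0.4/0.5 = 0.80.

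For fixed stays, P = 1 − exp(−rL) gives 39.3% and 33.0%, a risk ratio of 0.84. If the daily rate in the shorter-stay arm is truly 25% higher, rL is 0.0625 × 8 = 0.5 in that arm and 0.05 × 10 = 0.5 in the other. The proportions are equal and the excess is hidden.

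**Step 2: skewed stays and risk that falls over the admission.** Stay is lognormal with mean 7 and SD 9 days, rounded to whole days with a minimum of 1. Daily risk is p0·exp(−d·(day − 1)), and discharge is unrelated to risk. One arm's stay is 20% shorter. Ranges run over p0 of 0.02 to 0.10 for d = 0, 0.05 to 0.10 for d = 0.1, and 0.05 to 0.20 for d = 0.3.

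| Decline d per day | Example, longer vs shorter stay | OR, equal daily risk | OR, daily risk 25% higher in shorter-stay arm |
|---|---|---|---|
| 0 | 25.6% vs 21.7% (p0 0.05) | 0.80–0.81 | 1.01–1.02 |
| 0.1 | 18.7% vs 16.5% (p0 0.05) | 0.85–0.86 | about 1.10 |
| 0.3 | 23.7% vs 22.0% (p0 0.10) | 0.90–0.92 | 1.17–1.22 |

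With equal stays, the 25% higher daily risk would show as an OR of 1.25 to 1.37. It is fully masked only under constant risk. With a stay 10% shorter, the equal-risk ORs are 0.90, 0.93 and 0.95–0.96. Changing the stay distribution (mean 4 SD 5 to mean 14 SD 14, 20% shorter) gives 0.77–0.81, 0.85–0.88 and 0.89–0.95.

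**Step 3: does a patient-day rate do better?** An unbanded rate ratio (events over patient-days, shorter-stay arm over longer) is 1.00 under constant risk. When risk is highest early, a shorter stay concentrates patient-days in the high-risk period. With no true difference, d = 0.3 and a 20% shorter stay, the ratio is 1.12 (mean 4 SD 5), 1.15 (mean 7 SD 9) and 1.19 (mean 14 SD 14).

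Banding by day of admission (1, 2, 3–4, 5–7, 8–14, 15+) brings the ratio back to 1.00–1.01 when discharge is unrelated to risk. If patients at higher risk also stay longer (correlation 0.3 to 0.6 between log risk and log stay, SD of log risk 0.7), the banded ratio drifts to 1.01–1.06.

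**The case against.** The strongest reply is that nothing here is an error. The proportion compares randomised groups on what happens over an admission, and §5.3 never calls it a daily risk. A rate per patient-day conditions on a post-randomisation quantity, and with early-peaking risk it can be further from the truth than the proportion: 1.15 against 0.90–0.92 in the mean 7, SD 9 example. This stands, and it is why the proportion should stay.

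It is also fair that the harms in question are an unlisted remainder, and that the published protocol may define event types, dating and window. Some important in-hospital harms (suicide risk, continuous observation, aggression) already have day-level models as secondary outcomes in §5.2, which limits the practical consequence.

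Three stronger readings are tempting and are not supported:
- **A reader might infer that chi-squared is the sole analysis.** It is not. Poisson regression is mentioned, and nothing excludes an offset; the text leaves it unstated.
- **A reader might infer that ward transfer escapes the problem because it happens once.** A shorter stay also leaves less opportunity for transfer. A proportion is acceptable there for the same reason as elsewhere, with the same label.
- **A reader might extend the point to §5.2.2**, where daily binary outcomes are such that "these variables may be simplified into a single binary variable across the entire admission". That simplification is optional and tied to convergence and event frequency, so it is not a fault of the plan.

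The objection does not remove the need to state the exposure term and to say what the proportion measures.

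**Conclusion.** The point holds as a minor one. §5.3 sets a default comparison whose time at risk is the quantity the trial expects to change, and it names no exposure term for the default or the alternative. The per-admission proportion is valid as cumulative risk. If stays differ, it cannot be read as a difference in daily risk or tolerability.

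The direction follows from the design; the size rests wholly on assumed inputs. With a 20% shorter stay (mean 7, SD 9), the equal-risk odds ratio is about 0.80 to 0.92. At 10% shorter it is 0.90 to 0.96, and with no difference in stay the issue disappears. The reading assumes that events are counted over the admission, which the wording of the Poisson sentence suggests but §5.3 does not define. The primary analysis is not affected.

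**What to change.** In §5.3:
1. Keep the proportion, including for ward transfer, and label it as per-admission risk that includes any effect on length of stay.
2. Beside it, report adverse events per patient-day by arm, with a rate ratio and 95% CI. The interval should allow for repeat admissions of the same patient, since §5.1 notes: "Some patients will be readmitted and re-randomized during the study period".
3. Specify log patient-days as the offset in any Poisson model.
4. Where event dates exist, stratify the rate by day-of-admission bands.
5. State that the proportion and the rate are to be read together.

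The cost is a few sentences and minor programming. The denominators should be available, since §5.1.1 says: "The primary outcome is based on hospital records of date of admission and date of discharge and will have no missing data". The downsides are that banding needs event dates, which this SAP does not describe, and that an unbanded rate ratio can err the other way when risk is highest early.
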